4.2. Inclusion Criteria

Subjects must meet all of the following inclusion criteria to be eligible for participation in this study.

1. Must have the ability to understand and sign a written informed consent form, which must be obtained prior to initiation of study procedures.
2. Male and non-pregnant, non-lactating female subjects, 18 years of age and older, based on the date of the screening visit. A negative serum pregnancy test at Screening is required for female subjects of childbearing potential (as defined in [Appendix 6](#)).
3. Documented evidence of chronic HBV infection (e.g. HBsAg positive for more than 6 months).
4. HBeAg-negative, chronic hepatitis B with all of the following:
 - HBeAg-negative and HBeAb-positive at Screening (if the subject is deemed ineligible for this study by HBV serology [i.e. HBeAg-positive CHB], this information may be used to determine eligibility for GS-US-320-0110 [another Gilead Sciences Phase 3 study in HBeAg-positive, CHB subjects; this study must also be IRB/EC approved at the participating center])
 - Screening HBV DNA $\geq 2 \times 10^4$ IU/mL
 - Screening serum ALT level > 60 U/L (males) or > 38 U/L (females) and $\leq 10 \times$ ULN (by central laboratory range)

5. Treatment-naïve subjects (defined as < 12 weeks of oral antiviral treatment with any nucleoside or nucleotide analogue), **OR** treatment-experienced subjects (defined as subjects meeting all entry criteria [including HBV DNA and serum ALT criteria] and with ≥ 12 weeks of previous treatment with any nucleoside or nucleotide analogue) will be eligible for enrollment. Treatment-experienced subjects receiving oral antiviral treatment at Screening must continue their treatment regimen until the time of randomization, when it will be discontinued.
6. Any previous treatment with interferon (pegylated or non-pegylated) must have ended at least 6 months prior to the baseline visit.
7. Estimated creatinine clearance (CL_{Cr}) ≥ 50 mL/min (using the Cockcroft-Gault method) based on serum creatinine and actual body weight as measured at the Screening evaluation, as follows:

$$\frac{(140 - \text{age in years}) (\text{body weight [kg]})}{(72) (\text{serum creatinine [mg/dL]})}$$

[Note: multiply estimated rate by 0.85 for women]

8. Normal ECG (or if abnormal, determined by the investigator not to be clinically significant)
9. Must be willing and able to comply with all study requirements.

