6.2. Pretreatment Assessments

6.2.1. Screening Visit

Subjects will be screened within 45 days before Baseline to determine eligibility for participation in the study. The following will be performed and documented during the screening period:

- Obtain written informed consent
- Review of inclusion/exclusion criteria
- Obtain medical history, including HBV history
- Review concomitant medications
- Record any serious adverse events and all adverse events related to protocol mandated procedures occurring after signing of the consent form
- Complete physical examination including vital signs (blood pressure, pulse, respiration rate and temperature), body weight, and height

- ECG (subjects must rest quietly in the supine position for a minimum of 5 minutes prior to the recording)
- DXA scan of spine and hip (at sites in China with capability only). DXA scan will be performed at any time during the Screening period and should be completed at least 14 days prior to the first dose of the study drug, in order to ensure an acceptable pre-dose DXA scan
- Ophthalmologic assessment, including fundoscopic examination with slit lamp and retinal photographs (both eyes) (**substudy subjects only at select sites** - separate consent required) – to be performed at any time during the Screening period and prior to the first dose of the study drug
- Blood sample for serum chemistry and liver function tests, hematology, plasma HBV DNA, serum HBsAg (quantitative), HBV serology (HBeAg, HBeAb, HBsAg and reflex HBsAb), HIV-1, HDV, HCV, serum pregnancy test (for females of child-bearing potential), α -fetoprotein (AFP) and INR. An AFP > 50 ng/mL at Screening must have an appropriate evaluation (e.g. CT scan) in order to rule out HCC prior to being permitted to enter the study
- Estimated creatinine clearance (using the Cockcroft-Gault method)
- Urine sample for urinalysis

Subjects meeting all of the inclusion criteria and none of the exclusion criteria will return to the clinic within 45 days for randomization into the study. If the subject is deemed ineligible for this study by HBV serology (i.e. HBeAg-positive CHB), this information may be used to determine eligibility for GS-US-320-0110 (another Gilead Sciences Phase 3 study in HBeAg positive, CHB subjects; this study must also be IRB/EC approved at the participating center).

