For subjects who completed blinded study drug and entered open-label phase, the **Last Dose Date** is the latest non-missing end date of open-label study drug, recorded on the Study Drug Administration eCRF form with “Study Drug Permanently Discontinued” box checked for subjects who prematurely discontinued open-label study drug or who completed open-label study drug according to Open-Label Study Drug Completion eCRF. If the last dose date is missing (eg, due to lost to follow up) for subjects who prematurely discontinued open-label study drug, or for subjects who are still on open-label study drug, the latest of nonmissing open-label study drug start dates and end dates, the clinical visit dates and the laboratory visit dates excluding the dates of 24-week treatment-free follow-up visits will be used to impute the last dose date.

Last Study Date is the latest of nonmissing study drug (blinded or open-label) start dates and end dates, the clinic visit and the laboratory visit dates including the 24-week treatment-free follow-up visit date for subjects who prematurely discontinued study or who completed study according to Study Completion eCRF.

Baseline value is defined as the last nonmissing value obtained on or prior to Study Day 1. For DXA BMD, it is defined as the last value on or prior to Study Day 14.

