6.2. Secondary Efficacy Endpoints

6.2.1. Definition of Secondary Efficacy Endpoints

The secondary efficacy endpoints are as follows:

- The proportion of subjects with plasma HBV DNA < 29 IU/mL at Weeks 96, 144, 240, and 384
- The proportion of subjects with plasma HBV DNA < 29 IU/mL (target not detected) at Weeks 48, 96, 144, 240, and 384
- The proportion of subjects with ALT normalization (by central laboratory and AASLD criteria) at Weeks 48, 96, 144, 240, and 384
- The proportion of subjects with HBsAg loss at Weeks 48, 96, 144, 240, and 384
- The proportion of subjects with HBsAg seroconversion to anti-HBs at Weeks 48, 96, 144, 240, and 384
- The change from baseline in fibrosis as assessed by FibroTest[®] at Weeks 48, 96, 144, 240, and 384
- The incidence of drug resistant mutations at Weeks 48, 96, 144, 240, and 384
- The change from baseline in log₁₀ (HBV DNA) (IU/mL) at Weeks 48, 96, 144, 240, and 384
- The change from baseline in log₁₀ (HBsAg) (IU/mL) at Weeks 48, 96, 144, 240, and 384
- The change from baseline in ALT at Weeks 48, 96, 144, 240, and 384

The secondary endpoints beyond Week 96 (Weeks 144, 240, and 384) will not be summarized for the Week 48 analysis. Incidence of drug resistant mutations will be reported in a separate virology report.

For the Week 48 analysis, the following definitions will be used:

- HBsAg loss is defined as HBsAg test result changes from HBsAg positive at baseline to HBsAg negative at a postbaseline visit with baseline HBsAb negative or missing
- HBsAg seroconversion is defined as HBsAg loss and HBsAb test result changes from HBsAb negative or missing at baseline to HBsAb positive at a postbaseline visit
- ALT normalization is defined as ALT > ULN (by central laboratory normal range or AASLD normal range) at baseline but within normal range at a postbaseline visit

Both baseline and postbaseline borderline serology results will be imputed using the following rules:

- HBsAg and HBeAg borderline will be considered as HBsAg positive and HBeAg positive
- HBsAb and HBeAb borderline will be considered as HBsAb negative and HBeAb negative

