6.2.2. Analysis Methods for Secondary Efficacy Endpoints

The analyses for the secondary efficacy endpoints will be conducted using the FAS.

All the secondary efficacy endpoints involving proportions will be analyzed using the same statistical method ($M = F$) applied to the analysis of the primary efficacy endpoint. Sensitivity analyses will be performed using the $M = E$ approach as well.

The change from baseline in \log_{10} (HBV DNA) (IU/mL), \log_{10} (HBsAg) (IU/mL), and ALT will be summarized by visit using observed data (ie, missing will be excluded). In addition, the proportion of subjects with HBV DNA < 29 IU/mL, mean change from baseline in \log_{10} (HBV DNA) (IU/mL), \log_{10} (HBsAg) (IU/mL), and ALT (U/L) will be plotted with 95% CI over time using observed data for FAS.

Fibrosis assessed by FibroTest[®] at each visit and the change from baseline in fibrotest score will be summarized using descriptive statistics (sample size, mean, SD, median, Q1, Q3, minimum, and maximum) by treatment group. A shift table of fibrosis stage based on fibrotest score by visit will also be provided. Mean change from baseline in fibrotest score will be plotted with 95% CI over time using observed data for FAS. A listing of fibrosis assessment by FibroTest[®] will also be provided.

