21.1.1	Proportion of Subjects with Normal ALT by Visit by Central Lab Normal Range (Missing = Failure)	Full Analysis Set
21.1.2	Proportion of Subjects with Normal ALT by Visit by Central Lab Normal Range (Missing = Excluded)	Full Analysis Set
21.2.1	Proportion of Subjects with Normal ALT by Visit by AASLD Normal Range (Missing = Failure)	Full Analysis Set
21.2.2	Proportion of Subjects with Normal ALT by Visit by AASLD Normal Range (Missing = Excluded)	Full Analysis Set
22.1.1	Proportion of Subjects with ALT Normalization by Visit by Central Lab Normal Range (Missing = Failure)	Full Analysis Set with Baseline ALT > ULN
22.1.2	Proportion of Subjects with ALT Normalization by Visit by Central Lab Normal Range (Missing = Excluded)	Full Analysis Set with Baseline ALT > ULN
22.2.1	Proportion of Subjects with ALT Normalization by Visit by AASLD Normal Range (Missing = Failure)	Full Analysis Set with Baseline ALT > ULN
22.2.2	Proportion of Subjects with ALT Normalization by Visit by AASLD Normal Range (Missing = Excluded)	Full Analysis Set with Baseline ALT > ULN
23	ALT (U/L) and Change from Baseline in ALT (U/L) by Visit	Full Analysis Set
24	Fibrotest Score and Change from Baseline in Fibrotest Score by Visit	Full Analysis Set
25	Shift Table of Fibrosis Stage by FibroTest® by Visit	Full Analysis Set
26	Treatment-Emergent Adverse Events: Overall Summary	Safety Analysis Set
27	Treatment-Emergent Adverse Events	Safety Analysis Set
28	Treatment-Emergent Nonserious Adverse Events Occurring in ≥ 5% of Subjects in Any Treatment Group	Safety Analysis Set
29	Grade 2, 3, or 4 Treatment-Emergent Adverse Events	Safety Analysis Set
30	Grade 3 or 4 Treatment-Emergent Adverse Events	Safety Analysis Set
31	Treatment-Emergent Study Drug-Related Adverse Events	Safety Analysis Set
32	Grade 2, 3, or 4 Treatment-Emergent Study Drug-Related Adverse Events	Safety Analysis Set
33	Grade 3 or 4 Treatment-Emergent Study Drug-Related Adverse Events	Safety Analysis Set
34	Treatment-Emergent Serious Adverse Events	Safety Analysis Set
35	Treatment-Emergent Study Drug-Related Serious Adverse Events	Safety Analysis Set
36	Treatment-Emergent Adverse Events Leading to Premature Study Drug Discontinuation	Safety Analysis Set
37	Treatment-Emergent Adverse Events Leading to Dose Modification or Study Drug Interruption	Safety Analysis Set
38	Treatment-Emergent Potential Uveitis Events	Safety Analysis Set
39	Treatment-Emergent Potential Cardiovascular Events	Safety Analysis Set

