6	Mean and 95% CIs of Change from Baseline in HBsAg (log ₁₀ IU/mL) by Visit (Observed Data)	Full Analysis Set
7.1	Proportion of Subjects with ALT Normalization by Visit by Central Laboratory Normal Range: Missing = Failure	Full Analysis Set
7.2	Proportion of Subjects with ALT Normalization by Visit by AASLD Normal Range: Missing = Failure	Full Analysis Set
8	Mean and 95% CIs of Change from Baseline in ALT (U/L) (Observed Data)	Full Analysis Set
9	Mean and 95% CIs of Change from Baseline in Fibrotest Score (Observed Data)	Full Analysis Set
10.1	Median (Q1, Q3) of Change from Baseline in Fasting Total Cholesterol (mg/dL) by Visit	Safety Analysis Set
10.2	Median (Q1, Q3) of Change from Baseline in Fasting Direct LDL (mg/dL) by Visit	Safety Analysis Set
10.3	Median (Q1, Q3) of Change from Baseline in Fasting HDL (mg/dL) by Visit	Safety Analysis Set
10.4	Median (Q1, Q3) of Change from Baseline in Fasting Total Cholesterol to HDL Ratio by Visit	Safety Analysis Set
10.5	Median (Q1, Q3) of Change from Baseline in Fasting Triglycerides (mg/dL) by Visit	Safety Analysis Set
10.6	Median (Q1, Q3) of Change from Baseline in Fasting Glucose (mg/dL) by Visit	Safety Analysis Set
11.1.1	Median (Q1, Q3) of Percentage Change from Baseline in Hip Bone Mineral Density by Visit (Observed Data)	Hip DXA Analysis Set
11.1.2	Median (Q1, Q3) of Percentage Change from Baseline in Spine Bone Mineral Density by Visit (Observed Data)	Spine DXA Analysis Set
11.2.1	Mean and 95% CIs of Percentage Change from Baseline in Hip Bone Mineral Density by Visit (Observed Data)	Hip DXA Analysis Set

Figure Number	Title	Analysis Set
11.2.2	Mean and 95% CIs of Percentage Change from Baseline in Spine Bone Mineral Density by Visit (Observed Data)	Spine DXA Analysis Set
12.1	Median (Q1, Q3) of Percentage Change from Baseline in Serum C-type Collagen Sequence (CTX) by Visit	Safety Analysis Set
12.2	Median (Q1, Q3) of Percentage Change from Baseline in Serum Bone Procollagen Type 1 N-terminal Propeptide (P1NP) by Visit	Safety Analysis Set
12.3	Median (Q1, Q3) of Percentage Change from Baseline in Serum Parathyroid Hormone (PTH) by Visit	Safety Analysis Set
12.4	Median (Q1, Q3) of Percentage Change from Baseline in Osteocalcin (OC) by Visit	Safety Analysis Set
12.5	Median (Q1, Q3) of Percentage Change from Baseline in Bone Specific Alkaline Phosphatase (bsAP) by Visit	Safety Analysis Set
13.1	Median (Q1, Q3) of Change from Baseline in Serum Creatinine (mg/dL) by Visit (Observed Data)	Safety Analysis Set

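### The two ALT-normalization figures and SAP 6.2.2 use the unrestricted FAS, while the matching tables use only subjects with raised baseline ALT, so figure and table can disagree

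*SAP*

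**What the plan says.** **Endpoint.** SAP 6.2.1 states: "ALT normalization is defined as ALT > ULN (by central laboratory normal range or AASLD normal range) at baseline but within normal range" at a later visit. Raised ALT at baseline is part of the definition.

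**Analysis set in the text.** SAP 6.2.2 states: "The analyses for the secondary efficacy endpoints will be conducted using the FAS". It makes no exception for ALT normalization.

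**Analysis set in the output list (SAP Appendix 1).**
- Tables 22.1.1 and 22.1.2 (central laboratory range) and 22.2.1 and 22.2.2 (AASLD range): "Full Analysis Set with Baseline ALT > ULN".
- Figure 7.1, "Proportion of Subjects with ALT Normalization by Visit by Central Laboratory Normal Range: Missing = Failure", and Figure 7.2, the same by AASLD range: Full Analysis Set, with no restriction.
- Tables 21.1.1 to 21.2.2, which report the different endpoint of having normal ALT: Full Analysis Set.

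**Entry and baseline.** Protocol 4.2, criterion 4, requires ALT above 60 U/L in men or 38 U/L in women, measured at Screening. Protocol 6.2.1 allows an interval before baseline: "Subjects will be screened within 45 days before Baseline to determine eligibility for participation in the study". The value used in analysis is a separate one. SAP 3.7.1 says: "Baseline value is defined as the last nonmissing value obtained on or prior to Study Day 1". No ALT threshold applies at baseline.

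**The concern.** A subject who entered with raised ALT may have ALT at or below ULN by Day 1. Treatment-experienced subjects already on an oral antiviral must continue it until randomization (Protocol 4.2, criterion 5), so a fall between the two visits is possible. The SAP provides for such subjects: at or below ULN is a subgroup level in 3.4 and a baseline category under both normal ranges in 5.1.

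Such a subject cannot normalize, even with normal ALT at every visit. The tables remove these subjects from the denominator and the figures, as labelled, keep them. One report would then carry two denominators for one endpoint, and two programmers following the SAP could produce different results. The figure would show a lower rate than the table that it illustrates.

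**Working it through.** The plan states no figure on this point, so there is nothing to reproduce. The check compares the two denominators.

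**Inputs**
- R: proportion normalized among subjects with baseline ALT above ULN, the rate in Tables 22.1.1 and 22.2.1. Not in the documents; assumed.
- f: share of the FAS with baseline ALT at or below ULN. Not in the documents; assumed.
- Arm sizes: about 100 TAF and 50 TDF (SAP 1.3).
- AASLD ULN: 30 U/L for men, 19 U/L for women (SAP 5.1). The central-laboratory ULN is not given.

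**Formula.** Subjects with baseline ALT at or below ULN contribute no responders, so:
- table rate = R
- figure rate on the unrestricted FAS = R × (1 − f)
- shortfall = R × f

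**Level, with R = 80%**

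| f | Table | Figure | Shortfall (points) |
|---|---|---|---|
| 0% | 80% | 80% | 0 |
| 5% | 80% | 76% | 4 |
| 10% | 80% | 72% | 8 |
| 15% | 80% | 68% | 12 |

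In counts for 100 TAF subjects at f = 10%: 90 can normalize and 0.80 × 90 = 72 do. The table shows 72/90 = 80% and the figure 72/100 = 72%.

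Over a wider range, R = 50% with f = 2% gives 1 point and R = 80% with f = 20% gives 16 points.

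**Difference between arms.** The figure shows R₁(1 − f₁) − R₂(1 − f₂).
- Equal R and equal f: the difference is 0, and only the level is too low.
- Equal f, different R: the difference is (R₁ − R₂)(1 − f), so a real difference shrinks slightly and no false one arises.
- Equal R, different f: an artificial difference of R × (f₂ − f₁) appears. With R = 80%, and 5 of 100 TAF and 5 of 50 TDF subjects at or below ULN (f = 5% and 10%), the figure shows 76% and 36/50 = 72%, a gap of 4 points. This imbalance is constructed for illustration.

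**The two figures separately.** To be at or below the AASLD limit at baseline, ALT must at least halve from the entry threshold: 30/60 = 0.5 in men, 19/38 = 0.5 in women. That fall must occur within the screening interval and before study drug. For Figure 7.2, f is therefore likely to be small. Figure 7.1 cannot be judged this way without the central-laboratory ULN.

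**Other figures in the list.** Each of these carries the same analysis set as its table: Figures 3.1 and 3.2 (Tables 14.1 and 14.2), 4 (15), 5 (17), 6 (20), 8 (23), 9 (24), and the BMD Figures 11.1.1 to 11.2.2 (48.1.2 and 48.2.2). Among the efficacy and BMD figures, only 7.1 and 7.2 depart from their tables.

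**The case against.** The best defence is that this is a label in one column of an output list. Section 6.2.2 names several quantities to be plotted, and ALT normalization is not among them, so no body text says how these figures are computed. The FAS sentence in 6.2.2 behaves like a general default: HBsAg loss is also a secondary endpoint, yet Appendix 1 puts it on the Serologically Evaluable FAS. The label may be shorthand, with the restriction understood from the definition and the tables, or it may come from the Normal ALT tables, where the whole FAS is correct.

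That explains how the label could have arisen, but does not settle which denominator to use. The list names restricted sets where they apply, including for figures, and nothing in the text overrides the label. The inconsistency stands. It remains an inference that the figures will be programmed as labelled.

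The other side is right about several stronger readings that a reader might infer:
- **That Missing = Failure makes these subjects failures.** It does not. That rule concerns missing values, and their later ALT may be observed. They are non-responders through the 6.2.1 definition combined with an unrestricted denominator.
- **That the SAP expects an appreciable number of them.** Listing a category shows only that it is possible. SAP 5.1 also lists HBeAg-positive status and ALT above 10 × ULN, both excluded at Screening.
- **That both figures are understated alike.** The AASLD arithmetic argues against this.
- **That a false treatment difference will appear.** This requires f to differ by arm. SAP 6.2.2 also plans no between-arm test on this endpoint, and Protocol 8.5.2 calls such comparisons exploratory.

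**Conclusion.** The point holds as a minor inconsistency in the plan. As written, Figures 7.1 and 7.2 and section 6.2.2 use a denominator that includes subjects who cannot meet the endpoint, while Tables 22.1.1 to 22.2.2 exclude them. If the listed set is used, the figure falls below its table by R × f. The illustrative 4 to 12 points for Figure 7.1 rest on assumed values (R = 80%, f = 5% to 15%). The actual size is unknown, and is zero if no subject has baseline ALT at or below ULN. Figure 7.2 may barely change.

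The documents do not support a claim of biased treatment comparison. These are descriptive plots of a secondary endpoint in the China Week 48 analysis, the correctly restricted tables appear in the same report, and neither the primary endpoint nor type I error is affected.

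**What to change.** 1. In SAP Appendix 1, change the analysis set of Figures 7.1 and 7.2 to the FAS with baseline ALT above ULN, by the matching range: central laboratory for 7.1, AASLD for 7.2. The set name in Tables 22.1.1 to 22.2.2 does not say which range applies, so add it there too.
2. In SAP 6.2.2, add one sentence saying that ALT normalization is analyzed on that subset.
3. Leave Tables 21.1.1 to 21.2.2 on the whole FAS, which is the right denominator for having normal ALT.

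The cost is a few words in the SAP and one filter in the figure program. No new data or outputs are needed, and each figure will then equal its Missing = Failure table (22.1.1 or 22.2.1).

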Appendix 2. Fracture Events

The selected PTs of fracture events from SMQ of Osteoporosis/Osteopenia and HLGT of Fractures are listed as follows:

	Selected Preferred Terms	Selection Type
1	Acetabulum fracture	cSMQ+cHLGT
2	Ankle fracture	cHLGT
3	Atypical femur fracture	cSMQ+cHLGT
4	Atypical fracture	cHLGT
5	Avulsion fracture	cHLGT
6	Bone fissure	cHLGT
7	Bone fragmentation	cHLGT
8	Cervical vertebral fracture	cSMQ+cHLGT
9	Chance fracture	cHLGT
10	Clavicle fracture	cHLGT
11	Closed fracture manipulation	cSMQ
12	Comminuted fracture	cHLGT
13	Complicated fracture	cHLGT
14	Compression fracture	cHLGT
15	Craniofacial fracture	cHLGT
16	Epiphyseal fracture	cHLGT
17	External fixation of fracture	cSMQ
18	Facial bones fracture	cHLGT
19	Femoral neck fracture	cSMQ+cHLGT
20	Femur fracture	cSMQ+cHLGT
21	Fibula fracture	cHLGT
22	Flail chest	cHLGT
23	Foot fracture	cHLGT
24	Forearm fracture	cSMQ+cHLGT
25	Fracture	cSMQ+cHLGT
26	Fracture displacement	cHLGT
27	Fracture of clavicle due to birth trauma	cHLGT
28	Fracture treatment	cSMQ
29	Fractured coccyx	cHLGT
30	Fractured ischium	cSMQ+cHLGT
31	Fractured sacrum	cSMQ+cHLGT
32	Fractured skull depressed	cHLGT
33	Greenstick fracture	cHLGT
34	Hand fracture	cHLGT
35	Hip fracture	cSMQ+cHLGT
36	Humerus fracture	cHLGT

	Selected Preferred Terms	Selection Type
37	Ilium fracture	cSMQ+cHLGT
38	Impacted fracture	cHLGT
39	Internal fixation of fracture	cSMQ
40	Jaw fracture	cHLGT
41	Limb fracture	cHLGT
42	Lower limb fracture	cHLGT
43	Lumbar vertebral fracture	cSMQ+cHLGT
44	Multiple fractures	cSMQ+cHLGT
45	Open fracture	cHLGT
46	Open reduction of fracture	cSMQ
47	Open reduction of spinal fracture	cSMQ
48	Osteochondral fracture	cHLGT
49	Osteoporotic fracture	cSMQ+cHLGT
50	Patella fracture	cHLGT
51	Pathological fracture	cSMQ+cHLGT
52	Pelvic fracture	cSMQ+cHLGT
53	Periprosthetic fracture	cHLGT
54	Pubis fracture	cSMQ+cHLGT
55	Radius fracture	cSMQ+cHLGT
56	Rib fracture	cSMQ+cHLGT
57	Sacroiliac fracture	cSMQ+cHLGT
58	Scapula fracture	cHLGT
59	Scapulothoracic dissociation	cHLGT
60	Skull fracture	cHLGT
61	Skull fractured base	cHLGT
62	Spinal compression fracture	cSMQ+cHLGT
63	Spinal fracture	cSMQ+cHLGT
64	Sternal fracture	cHLGT
65	Stress fracture	cHLGT
66	Tartrate-resistant acid phosphatase decreased	cSMQ
67	Thoracic vertebral fracture	cSMQ+cHLGT
68	Tibia fracture	cHLGT
69	Torus fracture	cHLGT
70	Traumatic fracture	cHLGT
71	Ulna fracture	cHLGT
72	Upper limb fracture	cHLGT
73	Vertebroplasty	cSMQ
74	Wrist fracture	cSMQ+cHLGT
75	Vertebral body replacement	cSMQ

